3.2 Secondary Endpoints

3.2.1 CR rate as defined above.

3.2.2 Minimal residual disease (MRD) negativity in subjects achieving a CR or CRh will be defined as less than 0.01% residual lymphoblasts by multiparameter flow cytometry.

3.2.3 2-year relapse-free survival (RFS) will be defined as the time from achieving CR or CRh to relapse defined as the reappearance of lymphoblasts in bone marrow or blood at >5% of cells or reappearance of extramedullary disease.

3.2.4 2-year overall survival (OS) will be defined as the time from starting study therapy to death from any cause.

3.2.5 ORR, CR rate, 2-year RFS, and 2-year OS in the Ph/BCR-ABL1-negative and Ph/BCR-ABL1-positive populations separately.

3.2.6 Allogeneic hematopoietic cell transplantation (HCT) rate in transplant-eligible subjects will be defined as the number of patients eligible for allogeneic HCT as determined by the investigator who actually proceed to transplant.

3.2.7 Safety and tolerability of blinatumomab in combination with pembrolizumab will be defined by treatment-emergent Grade 2-5 adverse events (AEs) defined using NCI CTCAE v4.03 toxicity criteria attributable to study therapy.

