Patients achieving a CR/CRh after 2 cycles will complete a total of 5 cycles of blinatumomab and pembrolizumab in the absence of relapse.

Patients not achieving a CR/CRh after 2 cycles of therapy or progressing after Day 15 of Cycle 1 will go off study.

Patients may proceed to allogeneic hematopoietic cell transplantation as consolidation any time after complete remission. Such patients will be censored for survival at time of initiation of conditioning regimen.

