5.9 Duration of Follow Up

Patients will be followed every 3 months for a minimum of **2 years** after removal from or completion of treatment or until death, whichever occurs first. Patients removed from treatment for unacceptable adverse events will be followed until resolution or stabilization of the adverse event then for relapse and survival afterwards.

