6.3 Follow-up Procedures

Patients will be followed for a minimum of 2 years from study entry or until death, whichever occurs first. Patients removed from study for unacceptable adverse events will be followed until resolution or stabilization of the adverse event. Patients taken off study to undergo allogeneic or autologous stem cell transplantation will be censored for relapse and survival as of the date they begin non-protocol therapy. Patients refusing protocol-defined follow-up or lost to follow-up will be censored as to their status on the day of last contact.

Patients will be seen every 3 months for 2 years after completion of therapy. At these visits the following assessment will be performed:

Physical exam, vital signs, weight

Labs: CBC with differential

Concomitant Medications

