7.1.7 Overall Survival

Overall survival is defined as the duration of time from start of treatment to death from any cause.

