8.1 Adverse Event Monitoring

Adverse event data collection and reporting, which are required as part of every clinical trial, are done to ensure the safety of subjects enrolled in the studies as well as those who will enroll in future studies using similar agents. Adverse events are reported in a routine manner at scheduled times during a trial. Additionally, certain adverse events must be reported in an expedited manner to allow for optimal monitoring of patient safety and care.

As far as possible, each adverse event should be evaluated to determine:

- duration (start and end dates)
- severity (grade)
- seriousness
- relationship to study agent
- action taken (i.e., none, study agent modification, medical intervention)
- outcome (i.e., resolved without sequelae, resolved with sequelae, ongoing)

Adverse events monitoring begins after initiation of study treatment and ends 30 days following the last administration of study treatment or study discontinuation/termination, whichever is earlier.

Adverse events may also occur in screened subjects during any pre-allocation baseline period as a result of a protocol-specified intervention, including washout or discontinuation of usual therapy, diet, placebo treatment or a procedure.

Progression of the cancer under study is not considered an adverse event unless it is considered to be drug related by the investigator.

All adverse events will be recorded from the time the consent form is signed through 30 days following cessation of treatment and at each examination on the Adverse Event case report forms/worksheets. The reporting timeframe for adverse events meeting any serious criteria is described in **Section 8.3**.

All patients experiencing an adverse event, regardless of its relationship to study drug {or at least possibly related to the drug}, will be monitored until:

- the adverse event resolves or the symptoms or signs that constitute the adverse event return to baseline;
- any clinically significant abnormal laboratory values have returned to baseline;
- there is a satisfactory explanation other than the study drug for the changes observed; or
- death

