10.4 Evaluable Subjects and Subject Replacement

Stage 1 (Safety evaluation)

Evaluable subjects are defined as any patient receiving the combination of blinatumomab and pembrolizumab starting day 15 of Cycle 1. The DLT monitoring period will be 28 days starting Day 15 of Cycle 1. Subjects withdrawing from investigational treatment during the 28 day DLT monitoring period for a reason that is definitely unrelated to toxicity of the study agent (e.g. disease progression, patient withdrawal of consent) will be replaced for the safety analysis. 3-6 patients will be enrolled at in Stage 1 as determined by 3+3 rules. These patients will also be evaluated for efficacy.

Stage 2

Stage 2 of the study will include an expansion cohort of up to 21 additional subjects for a total of 24 subjects to evaluate the efficacy of the combination of blinatumomab and pembrolizumab. All patients receiving combination therapy starting day 15 of cycle 1 will be considered evaluable for overall response rate of entire population, RFS and OS.

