10.5.2 Secondary Analyses

Complete response rate, overall response rate (CR + CRh), MRD negativity rate in patients achieving a CR or CRh, allogeneic HCT rate, and rates of adverse events will be reported using descriptive statistics. Relapse-free survival and overall survival will be estimated using the Kaplan-Meier method. Correlation between PD-L1 and PD-L2 expression and response to the combination of blinatumomab and pembrolizumab and correlation of changes in PD-L1 and PD-L2 expression with cytokine response will be evaluated with Chi-squared analysis.

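### The off-study wording for non-responders and progressors in 5.1.3 conflicts with the survival follow-up required elsewhere; reconcile it so that 2-year OS is not exposed to early censoring

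*Combined protocol and SAP*

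**What the plan says.** Section 5.1.3 (Therapy) settles what happens to patients who do not benefit: "Patients not achieving a CR/CRh after 2 cycles of therapy or progressing after Day 15 of Cycle 1 will go off study". The sentence says nothing about censoring or the end of follow-up. The next paragraph of 5.1.3 does state a censoring rule for survival, but only for patients who go on to allogeneic transplant.

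Other sections treat the same patients differently:

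- 5.8 lists progression after Day 15 of Cycle 1 among the reasons for ending treatment, not the study.
- 5.9 requires 3-monthly follow-up for at least two years "after removal from or completion of treatment or until death, whichever occurs first".
- 6.3 says "Patients will be followed for a minimum of 2 years from study entry or until death, whichever occurs first", with no exception for non-response.
- 6.6 separates leaving study treatment from leaving the study. It lists progression as a reason but does not say which of the two it triggers.

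OS is a secondary endpoint: "2-year overall survival (OS) will be defined as the time from starting study therapy to death from any cause" (3.2.4), and 7.1.7 agrees. Under 10.4, "All patients receiving combination therapy starting day 15 of cycle 1 will be considered evaluable for overall response rate of entire population, RFS and OS". Under 10.5.2, "Relapse-free survival and overall survival will be estimated using the Kaplan-Meier method".

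On safety, 8.1 says that adverse event monitoring "ends 30 days following the last administration of study treatment or study discontinuation/termination, whichever is earlier". Later, the same section has all adverse events recorded until 30 days after treatment stops.

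**The concern.** A patient cannot be off study and in study follow-up at once, so a site has to choose which section to obey. Several passages make the literal choice plausible. Section 6.3 uses the off-study term together with survival censoring for transplant patients. Section 5.4 requires removal from the study when other anticancer therapy is needed, as it will be for many non-responders. Section 6.3 ties the 3-monthly visits to completion of therapy and does not mention removal. Section 11.6 has an off-study form due within a week. Elsewhere, in the toxicity tables of 5.7.1, the protocol uses a different term (off protocol therapy) for stopping treatment, so the wording in 5.1.3 is not obviously loose.

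At stake is the 2-year OS estimate. Surviving non-responders have the worst outlook in the trial. If their follow-up stopped on leaving, the censoring would be informative and the Kaplan–Meier curve beyond that point would rest on responders. Routine adverse event capture could also be cut short under one of the two rules in 8.1.

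**Working it through.** **Planned figure.** The plan gives no target, expected value or precision for 2-year OS, so there is none to reproduce. Its only design calculation is the two-stage response rule in 10.5.1 (stop at 7 or fewer of 18; reject at 11 or more of 24). This reproduces by exact binomial: type I error 0.0499, power 0.8014, early termination 0.8800. It is unaffected by this point.

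**What would happen if 5.1.3 were applied literally**

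Inputs from the documents:
- Non-responder median OS 3.1 months (1.2.1, historical phase 2 study, whole cohort).
- ORR p = 0.29 or 0.54 (10.5.1, null and alternative).
- Exit day: 42-day cycles (5.1.3) and the second-cycle marrow at Day 29 + 8 days (5.1.6) give a latest day of 42 + 37 = 79, so c = 79/30.44 = 2.60 months.

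Assumptions: exponential survival, responder median m = 10 to 20 months, and every surviving non-responder lost at Day 79.

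Formulas:
- S_N(t) = exp(−ln2 · t/3.1); S_R(t) = exp(−ln2 · t/m)
- Full follow-up: S(t) = p·S_R(t) + (1−p)·S_N(t)
- Kaplan–Meier limit with non-responders lost at c: S(c) · S_R(24)/S_R(c)

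Components: S_N(2.60) = 0.560 and S_N(24) = 0.005. For m = 10, S_R(2.60) = 0.835, S_R(24) = 0.189, ratio 0.227. For m = 20, these are 0.914, 0.435 and 0.476.

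| p | m (months) | S(c) | 2-year OS, full follow-up | 2-year OS, literal exit | Overstatement (points) |
|---|---|---|---|---|---|
| 0.29 | 10 | 0.640 | 5.8% | 14.5% | 8.7 |
| 0.54 | 10 | 0.709 | 10.4% | 16.1% | 5.6 |
| 0.29 | 20 | 0.662 | 13.0% | 31.5% | 18.6 |
| 0.54 | 20 | 0.751 | 23.7% | 35.8% | 12.0 |

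(Differences are taken before rounding.)

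Patients alive to be lost at Day 79: 24 × (1−p) × 0.560. This is 24 × 0.71 × 0.560 = 9.5 (40%) at p = 0.29 and 24 × 0.46 × 0.560 = 6.2 (26%) at p = 0.54.

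Sensitivity: with exit at 2.4 months and responder medians from 6.7 to 32.4 months, the overstatement is about 3 to 17 points at p = 0.54 and 4 to 26 points at p = 0.29. The upper median is the one implied, under exponential survival, by the historical 43% ORR and the medians of 6.7 and 3.1 months. Progressors may leave earlier, which enlarges the effect. With p = 0.29 and m = 12, the true value is 7.6%, against 19.2% with exit at 2.4 months and 22.3% with exit at 1 month.

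**Adverse event window.** In Cycle 2, blinatumomab ends on Day 28 and the second pembrolizumab dose falls on Day 36. Suppose that study exit coincides with the marrow assessment (Days 29–37).
- Exit on Day 29 is 1 day after the last blinatumomab, so 30 − 1 = 29 days of the window would be lost.
- Exit on Day 37 without the Day 36 dose loses 30 − 9 = 21 days.
- Exit on Day 37 with that dose loses 30 − 1 = 29 days.

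**The case against.** The strongest reply is that the plan, read as a whole, already keeps these patients under follow-up. Sections 5.9 and 6.3 do so without exception, and 10.4 includes them in the OS population. The stated censoring rules cover only transplant and refusal of, or loss to, follow-up. In 6.6, withdrawal of consent is the only reason expressly tied to ending follow-up. The protocol also mixes its terms: for unacceptable adverse events, 5.9 speaks of removal from treatment and 6.3 of removal from study, and both continue follow-up to resolution. The sentence sits under a therapy heading and can be read as off protocol therapy.

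Most of this stands, and it rules out three stronger inferences that a reader might draw:

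- *That the plan as written inflates 2-year OS.* It does not. No passage prescribes censoring for non-response or progression, and the bias is zero if 5.9 and 6.3 are followed.
- *That half to 70% of patients would be censored.* The expected share of non-responders is 46–71%, but on these assumptions about 44% of them have died by Day 79 and count as events. That leaves 26–40% of all patients.
- *That safety reporting would stop at once.* Sections 8.8.1, 8.8.1.1 and 8.8.1.2 set separate windows of 30 to 90 days for serious adverse events and events of clinical interest. Earlier cut-offs in the latter two are tied to new anticancer therapy, not to off-study status. The monitoring sentence in 8.1 can also be parsed so that 30 days run from either event, in which case an exit after the last dose costs nothing.

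The objection does not remove the conflict. The text still gives sites two instructions for the same patient, and 6.3 supplies a precedent for treating an off-study patient as censored.

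**Conclusion.** This is a real inconsistency in the current text that should be corrected, not an established bias. Section 5.1.3 conflicts with 5.8, 5.9, 6.3 and 10.4. Applied literally, it could remove about 6 to 10 of 24 patients from survival follow-up and overstate 2-year OS by about 6 to 19 points.

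That range depends on exponential survival, an assumed responder median of 10–20 months, one exit day for all, and complete loss of surviving non-responders. The documents give no responder survival, and the 3.1-month median comes from a whole historical cohort, not from patients with more than 50% blasts. The direction, upward, holds in every scenario examined.

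The two adverse event end-points in 8.1 are a second, smaller inconsistency, which mainly concerns routine adverse events. The primary response analysis is not touched, and OS is estimated without a test.

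**What to change.** 1. In 5.1.3, reconcile the sentence with 5.8, 5.9 and 6.3. State that these patients end protocol therapy, remain in survival follow-up under 5.9 and 6.3, and are not censored for OS at that point. Leave the treatment rule itself unchanged.
2. In 6.6, say for each listed reason whether it ends treatment only or also follow-up.
3. In 8.1, reconcile the two end-points so that leaving protocol therapy does not shorten the 30-day adverse event window, except on withdrawal of consent.
4. While editing, align the start of the two-year period, which 5.9 counts from the end of treatment and 6.3 from study entry.

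The cost is wording in an amendment and a note to sites. The survival follow-up and the 30-day adverse event record are already required, so no procedures or patients are added.

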6.6 Removal of Subjects from Study Treatment and Study

Patients can be taken off the study treatment and/or study at any time at their own request, or they may be withdrawn at the discretion of the investigator for safety, behavioral or administrative reasons. The reason(s) for discontinuation will be documented and may include:

1. Patient completed study treatment;
2. Patient voluntarily withdraws from treatment (follow-up permitted);
3. Patient withdraws consent (termination of treatment and follow-up);
4. Patient is unable to comply with protocol requirements;
5. Patient demonstrates disease progression;
6. Patient experiences toxicity that makes continuation in the protocol unsafe;
7. Treating physician judges continuation on the study would not be in the patient's best interest;
8. Patient becomes pregnant (pregnancy to be reported along same timelines as a serious adverse event);
9. Development of second malignancy (except for basal cell carcinoma or squamous cell carcinoma of the skin) that requires treatment, which would interfere with this study;
10. Lost to follow-up.

If a research subject cannot be located to document survival after a period of 2 years, the subject may be considered "lost to follow-up." All attempts to contact the subject during the two years must be documented.

7. Measurement of Effect

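### OS is defined as death from any cause but censored at transplant with no uncensored analysis planned, and RFS has two different event definitions

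*Combined protocol and SAP*

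**What the plan says.** **OS definition.** Section 3.2.4 says that 2-year OS "will be defined as the time from starting study therapy to death from any cause". Section 7.1.7 agrees: "Overall survival is defined as the duration of time from start of treatment to death from any cause". Neither mentions transplant.

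**Censoring.** Section 5.1.3 states: "Patients may proceed to allogeneic hematopoietic cell transplantation as consolidation any time after complete remission". The next sentence is: "Such patients will be censored for survival at time of initiation of conditioning regimen". Section 6.3 has a second version of the rule: patients who leave the study for an allogeneic or autologous transplant "will be censored for relapse and survival as of the date they begin non-protocol therapy".

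**RFS definition.** Section 3.2.3 runs the clock from CR or CRh to relapse and names no other event. Section 7.1.6 runs it from CR/CRh to relapse or death in CR. Section 7.1.5 already provides a relapse-only measure, duration of response.

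**Analysis.** Section 10.5.2 plans Kaplan-Meier estimates of RFS and OS. It names no uncensored, sensitivity or competing-risk analysis.

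**Follow-up.** Section 5.9 requires at least 2 years "after removal from or completion of treatment or until death, whichever occurs first". Section 6.3 opens with a minimum of 2 years from study entry, then says: "Patients will be seen every 3 months for 2 years after completion of therapy".

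**The concern.** A statistician who follows the plan must discard deaths after transplant that the OS definition counts. Kaplan-Meier then lets the patients still at risk stand in for those censored. That is sound only if the two groups have the same prognosis. Under 5.1.3 everyone censored is in remission, whereas the early risk set still contains non-responders, whose historical median OS was 3.1 months (1.2.1). The same censoring reaches RFS through the reference to relapse in 6.3.

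Section 1.3 gives more patients reaching allogeneic transplant as an intended benefit. The transplant rate is reported as its own endpoint (3.2.6), so that benefit is measured. What is lost is survival and relapse after transplant.

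The RFS mismatch is a separate matter. A death in remission is an event under one section and not under the other, so two analysts could report different 2-year figures from the same data.

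**Working it through.** **1. Is there a planned figure to reproduce?** No. The documents give no target, event count or power for OS or RFS. The only sized endpoint is the response rate. Its rule (stop at 7 or fewer of 18, reject at 11 or more of 24) gives exact type I error 0.0499, power 0.801 and early-stopping probability 0.880, matching the stated 0.05, 0.80 and 0.88. Nothing here depends on OS or RFS.

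**2. The two censoring rules side by side**

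| | 5.1.3 | 6.3 |
|---|---|---|
| Transplant type | allogeneic | allogeneic or autologous |
| Censoring date | start of conditioning | start of non-protocol therapy |
| Endpoints | survival | relapse and survival |

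The two dates may coincide in practice, but the plan does not say so.

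**3. Inputs for an illustration of 2-year OS**
- Non-responder median: 3.1 months (1.2.1).
- Responder median m. Section 1.2.1 gives an overall median of 6.7 months and a 43% response rate. Assuming an exponential mixture, 0.57 × 2^(-6.7/3.1) + 0.43 × 2^(-6.7/m) = 0.5. The first term is 0.127, so m = 32.4; 32 is used. This is fitted to the whole historical population, not the high-blast group, and its responders may include transplanted patients. A 12-month median is therefore run as an alternative assumption.
- Response rate R: 0.46 (11/24, the rejection boundary) and 0.54 (the design value).
- Assumed: a share q of 30%, 50% or 70% of responders transplanted, uniformly between 2.5 and 5 months. That is 24 × 0.46 × 0.30 = 3.3 to 24 × 0.54 × 0.70 = 9.1 patients, before any deaths ahead of transplant.

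**4. Formulas.** Let N(t) = (1-R) × 2^(-t/3.1), P(t) = R × 2^(-t/m), and U(t) = the share of planned transplants done by month t. The censored Kaplan-Meier curve tends to exp(-∫h), with

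h = [a·N + b·P(1-qU)] / [N + P(1-qU)], a = ln2/3.1, b = ln2/m.

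**5. Selection alone (transplant does not change the risk of death).** True 2-year OS is N(24) + P(24). For R = 0.54 and m = 32 this is 0.002 + 0.321 = 32.3%.

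| m | R | True | Censored, q = 30 / 50 / 70% | Difference (points) |
|---|---|---|---|---|
| 32 | 0.46 | 27.6% | 24.1 / 20.7 / 15.7% | -3.5 / -6.9 / -12.0 |
| 32 | 0.54 | 32.3% | 28.9 / 25.5 / 20.0% | -3.4 / -6.9 / -12.3 |
| 12 | 0.46 | 11.8% | 10.2 / 8.7 / 6.6% | -1.6 / -3.1 / -5.2 |
| 12 | 0.54 | 13.7% | 12.2 / 10.7 / 8.3% | -1.5 / -3.1 / -5.4 |

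**6. Net difference when survival after transplant differs.** Let s be 2-year post-transplant survival. True OS becomes N(24) + R × [(1-q) × 2^(-24/m) + q × mean over transplant month u of 2^(-u/m) × s^((24-u)/24)]. The range for s is assumed to be 16-70%. The low end borrows the 5-year matched-unrelated-donor figure in 1.1.1 as a floor; the rest has no source in the documents. The range includes values above and below the 2-year survival implied for untransplanted responders, which is 2^(-24/32) = 59% or 2^(-24/12) = 25%.

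| s | m = 32 | m = 12 |
|---|---|---|
| 16% | +0.9 to +3.9 | -2.7 to -0.3 |
| 50% | -9.4 to -2.1 | -12.9 to -4.3 |
| 70% | -15.6 to -4.7 | -18.5 to -6.3 |

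**7. Sampling error.** An observed 6/24 (25%) has an exact 95% interval of 10% to 47%.

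**8. RFS events.** Counting relapse only can never give a lower curve than counting relapse or death. As an unsourced example, with 50% relapse and 15% death in remission by 2 years and proportional hazards, 7.1.6 gives 35% and 3.2.3 gives 0.35^(0.50/0.65) = 45%.

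**The case against.** The strongest defence is that this is a choice of estimand: the definitions fix the event and the clock, the censoring rule is stated in advance in two places, and together they describe survival on protocol therapy without transplant. That stands to this extent: a planned rule is not an error in itself, and a censored curve can be worth having. It fails as a full answer. The definitions never mention transplant, and censoring would isolate the regimen only if it were unrelated to prognosis, which 5.1.3 rules out by tying it to remission.

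It is also fair to say that these are descriptive secondary endpoints in 24 patients with no test or decision attached. That limits the severity, but more patients would not cure the mismatch.

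On cost, the existing follow-up text is not fully clear. Section 6.3 speaks of transplant patients being taken off study, and the item in 6.6 that permits follow-up covers voluntary withdrawal from treatment, not transplant. The gap over death in CRh is minor, since 7.1.4.1 defines CRh as CR with lower counts.

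A reader might infer that the reported OS will be biased in a known direction. The documents do not support that: selection pulls the censored estimate down, but poor survival after transplant can push the net difference above zero.

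**Conclusion.** The textual conflicts are certain. Under the plan, 2-year OS and RFS would not estimate the endpoints as defined, no analysis keeps events after transplant, and RFS has two event definitions.

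The size is illustrative only. If transplant had no effect on the risk of death, censored 2-year OS would be too low by about 3 to 12 points with a 32-month responder median, or about 1.5 to 5.5 points with 12 months. With post-transplant 2-year survival of 16-70%, the net difference runs from about -16 to +4 points at 32 months and from about -19 to 0 at 12 months. These figures rest on exponential survival and on assumed transplant shares, timing and outcomes. Sampling error exceeds most of them.

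A reader might go further and conclude that the trial's main result is compromised or that transplant is ignored. Neither follows. The response-rate test, sample size and stopping rules do not use OS or RFS, and the transplant rate is a reported endpoint. This should be corrected, but it does not undermine the design.

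**What to change.** - **5.1.3, 6.3 and 10.5.2:** report OS (death from any cause) and RFS without censoring at transplant, as the analyses that match the definitions. Keep transplant-censored curves as labelled sensitivity analyses, with one stated censoring date and transplant type.
- **3.2.3:** align with 7.1.6, so that RFS counts relapse or death in remission, and say that remission means CR or CRh.
- **5.9 and 6.3:** reconcile 2 years after removal from or completion of treatment with 2 years from study entry. The latter need not cover 2-year RFS, whose clock starts later, at CR/CRh. State that leaving the study for transplant means leaving treatment only, so that follow-up for relapse and death continues.

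**Cost.** Sample size and the response-rate analysis do not change. In the plan this is mostly wording, but sites must keep collecting relapse and survival status after transplant. The main estimates will then reflect the regimen plus any later transplant, which the text should say.
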